1. SYNOPSIS

Title:

A Randomized, Double-Blind, Vehicle Controlled, Proof of Concept Study of the Safety and Efficacy of ACU-D1-201 Ointment [REDACTED] in Subjects with Acne Rosacea.

Objectives:

The main objective of this study is to evaluate the safety, tolerability and efficacy of ACU-D1 Ointment [REDACTED] when applied twice daily for 12 weeks to papulopustular, Type-2, rosacea (acne rosacea) of the face.

Methodology/Study Design:

This study incorporates a randomized, double-blind, vehicle controlled, parallel-group design.

During this study, the subjects will apply ACU-D1 Ointment [REDACTED] or ACU-D1 Ointment Vehicle to acne rosacea of the face twice daily during a 12-week treatment period.

Approximately 36 subjects will be assigned to a study medication treatment group in a 2:1 ratio (24 to ACU-D1 Ointment [REDACTED]; 12 to ACU-D1 Ointment Vehicle) at multiple United States investigational centers.

The duration of study participation is anticipated to be a maximum of 116 days per subject. The final study visit (Visit 7) has a maximum allowable visit window of 4 days.

Study visits are:

- Visit 1 (Day -13 to 0) enrollment and start of the screening period
- Visit 2 (Day 1) randomization and start of the study medication treatment period
- Visit 3 (Day 15) treatment period follow-up
- Visit 4 (Day 29) treatment period follow-up
- Visit 5 (Day 57) treatment period follow-up
- Visit 6 (Day 85) end of the treatment period and start of the no treatment follow-up period
- Visit 7 (Day 99) no treatment follow-up, end of study.

During Visit 1, the investigator determines eligibility of potential subjects for study enrollment and will, for eligible subjects, conduct the procedures to determine her/his eligibility for randomization.

At Visit 2, eligible subjects will be randomized to a study medication treatment group, will initiate twice daily applications for the 12-week treatment period and will perform the first study medication while being observed by an investigational center staff member.

At Visits 3-5, subjects will be seen for treatment period follow-up.

At Visit 6, subjects will be seen for end of the treatment period follow-up and will start the 2-week no treatment follow-up period.

At Visit 7, subjects will be seen for a no treatment follow-up and be discharged from the study.

Number of Subjects:

Approximately 36 subjects will be enrolled in this study at multiple United States investigational centers. Subjects will be randomized in a 2:1 ratio with the goal to have 24 subjects randomized to treatment with ACU-D1 Ointment [REDACTED] and 12 subjects randomized to treatment with ACU-D1 Ointment Vehicle.

Diagnosis and Main Criteria for Inclusion:

Subjects will be adult males and females with a clinical diagnosis of papulopustular rosacea of the face that includes a total of ≥ 10 and ≤ 40 papules, pustules and nodules with ≤ 2 nodules.

Study Medications, Application, and Mode of Administration:

There are 2 study medications:

- ACU-D1 Ointment [REDACTED]
- ACU-D1 Ointment Vehicle.

There are 2 treatment groups:

- ACU-D1 Ointment [REDACTED] applied twice daily for 12 weeks
- ACU-D1 Ointment Vehicle applied twice daily for 12 weeks.

Subjects will be assigned to one of the two treatment groups, in a blinded manner, in a 2:1 ratio, 24 subjects will be assigned to receive ACU-D1 Ointment [REDACTED] and 12 subjects will be assigned to receive ACU-D1 Ointment Vehicle.

Subjects will apply the assigned study medication twice daily during a 12-week treatment period.

Duration of Study:

The planned treatment and study durations are:

- Enrollment period: approximately 84 days (12 weeks)
- Subject participation period: up to 116 days
- Study duration (first subject first visit, through last subject last visit): approximately 200 days.

Evaluations – Efficacy:

The investigator will perform a Lesion Count of papules, pustules and nodules and an Investigator's Global Assessment (IGA), a static assessment of the average overall severity of papulopustular rosacea on the face, to evaluate the status of the rosacea throughout the study.

Evaluations – Safety:

Adverse events, local tolerability of signs and symptoms of irritation, clinical laboratory safety tests, vital sign readings and urine pregnancy tests will be monitored throughout the study.

Evaluations – Other:

Standardized color photographs of the subject's face to document the status of the rosacea being treated will be taken throughout the study.

Statistical Methods:

The goal of the statistical analysis is to assess evidence of an overall effect of twice-daily ACU-D1 in the therapy of subjects with papulopustular rosacea. Next a set of planned pair-wise comparisons will be made evaluating the active dose against vehicle. Two types of study populations will be analyzed, namely, the Intention-To-Treat (ITT) and the Per-Protocol populations. The definitions of the populations for the different types of analyses follow those given in the ICH E9 guideline (1998).

Safety analyses will include descriptive statistics calculated on the safety parameters using the ITT population. The proportion of subjects with treatment-emergent adverse events will be tabulated and presented by Medical Dictionary for Regulatory Activities (MedDRA) System Organ Class. Vital signs, Local Tolerability Assessment (LTA) scores and clinically relevant abnormal laboratory results will also be tabulated and presented. Where applicable data will be listed and summarized by visit.

Safety summaries will include listings of adverse event incidences within each MedDRA System Organ Class, and changes from pre-application values in vital signs. Adverse event summaries will be presented showing the proportion of subjects experiencing adverse events, both overall and by MedDRA System Organ Class.

LIST OF ABBREVIATIONS AND DEFINITIONS OF TERMS

Abbreviation	Term
AE	Adverse Event
ALT	Alanine aminotransferase
ANCOVA	Analysis of covariance
ANOVA	Analysis of variance
AST	Aspartate aminotransferase
BUN	Blood Urea Nitrogen
°C	Degrees Celsius
CFR	Code of Federal Regulations
CR	Clinically Relevant
CRA	Clinical Research Associate
CRO	Contract Research Organization
e.g.	for example (Latin; exempla gratia)
°F	Degrees Fahrenheit
FDA	Food and Drug Administration
G	Gram
GCP	Good Clinical Practice
HIPAA	Health Insurance Portability and Accountability Act of 1996
IB	Investigator's Brochure
ICF	Informed Consent Form
ICH	International Conference on Harmonization
i.e.	that is
Inc.	Incorporated
IGA	Investigator's Global Assessment
IRB	Institutional Review Board
LDH	Lactate dehydrogenase
LTA	Local Tolerability Assessment
MedDRA	Medical Dictionary for Regulatory Activities
MITT	Modified intent-to-treat
mL	Milliliter

Abbreviation	Term
NCR	Not Clinically Relevant
OTC	Over-the-counter
SAE	Serious Adverse Event
SAS	Statistical Analyses System
SI	Subject Identifier
SOP	Standard Operation Procedure
US	United States
WOCBP	Woman of childbearing potential

2. INTRODUCTION

2.1. Introduction and Background

Rosacea is one of the most commonly occurring dermatoses treated by dermatologists today. Rosacea is an inflammatory condition of the skin, classically presenting with flushing and/or blushing along with erythema, edema, telangiectasia, papules, pustules and nodules of the face.¹

ACU-D1 [pentaerythritol tetrakis (3-(3,5-di-tert-butyl-4-hydroxyphenyl) propionate) (PTTC)] may be beneficial in the treatment of inflammatory lesions in patients with rosacea based on its anti-inflammatory properties.

2.2. Study Rationale

This study is designed to evaluate the safety and efficacy of ACU-D1 Ointment (PTTC) [REDACTED] and a matching ointment vehicle in the treatment of the inflammatory lesions of the face associated with Type-2 (papulopustular) rosacea.

3. STUDY OBJECTIVES

The main objective of this study is to evaluate the safety, tolerability and efficacy of ACU-D1 Ointment [REDACTED] when applied twice daily for 12 weeks to papulopustular (Type-2) rosacea (acne rosacea) of the face.

4. SELECTION AND DISPOSITION OF STUDY POPULATION

4.1. Number of Subjects

Approximately 36 subjects will be enrolled in this study at multiple United States investigational centers. Subjects will be randomized in a 2:1 ratio with 24 subjects randomized to treatment with ACU-D1 Ointment [REDACTED] and 12 subjects randomized to treatment with ACU-D1 Ointment Vehicle. Subject enrollment will be competitive.

4.2. Study Population Characteristics

Male and female subjects, 18 years of age or older who meet all the inclusion criteria and none of the exclusion criteria will be allowed to enroll in this study.

4.3. Inclusion Criteria

To be eligible for enrollment at Visit 1 the subject must fulfill all the following inclusion criteria:

1. Subject is at least 18 years of age
2. Subject has a clinical diagnosis of stable papulopustular rosacea (type-2)
3. Subject has a total of ≥ 10 and ≤ 40 inflammatory lesions (papules, pustules and nodules) on the face
4. Subject has a ≤ 2 nodules on the face
5. Subject has an Investigator's Global Assessment score of ≥ 3
6. If the subject is a woman of childbearing potential, she has a negative urine pregnancy test and agrees to use an approved effective method of birth control for the duration of the study
7. Subject is non-pregnant and non-lactating
8. Subject is in good general health and free of any known disease state or physical condition which, in the investigator's opinion, might impair evaluation of rosacea or which exposes the subject to an unacceptable risk by study participation
9. Subject is willing and able to follow all study instructions and to attend all study visits
10. Subject is able to comprehend and willing to sign an Informed Consent Form.

4.4. Exclusion Criteria

Any potential subject who meets one or more of the following criteria will not be included in this study:

1. Subject is pregnant, nursing or planning to become pregnant during the duration of the study
2. Subject has used systemic glucocorticosteroids within 42 days prior to Visit 1 (inhaled and ocular glucocorticosteroids are permitted)
3. Subject has used systemic antibiotics within 28 days prior to Visit 1
4. Subject has used any topical glucocorticosteroids on the face within 28 days prior to Visit 1
5. Subject has used any prescription or over-the-counter (OTC) product for the treatment of acne or rosacea within 14 days prior to Visit 1
6. Subject is currently using any therapy that, in the investigator's opinion, is a photosensitizer (*e.g.*, phenothiazines, amiodarone, quinine, thiazides, sulphonamides, quinolones, etc.)
7. Subject currently has any skin disease (*e.g.*, psoriasis, atopic dermatitis, eczema), or condition (*e.g.*, actinic keratosis, photo-damage, sunburn, excessive hair, open wounds) that, in the investigator's opinion, might impair evaluation of rosacea or which exposes the subject to an unacceptable risk by study participation

8. Subject currently has, on the face, or has had on the face, any of the following within the specified period prior to Visit 1 that, in the investigator's opinion, might impair evaluation of rosacea or which exposes the subject to an unacceptable risk by study participation:
 - A cutaneous malignancy; 180 days
 - Experienced a sunburn; 14 days
9. Subject has facial hair, that in the investigator's opinion, might impair evaluation of rosacea or proper study medication application
10. Subject has a history of sensitivity to any of the ingredients in the study medications
11. Subject has participated in an investigational drug trial in which administration of an investigational study medication occurred within 30 days prior to Visit 1.

4.5. Previous and Concomitant Therapies

4.5.1. Previous therapies

During Visit 1, subjects will be questioned to ensure they have not used any excluded therapies.

4.5.2. Concomitant therapies

Concomitant therapies are any new or existing therapy received by the subject after signing the ICF until discharge from the study.

Concomitant therapies include drug (*e.g.*, prescription and OTC) and non-drug (*e.g.*, chiropractic, physical therapy, energy-based treatments) therapies. Subjects will refrain from receipt of any therapy in accord with the inclusion/exclusion criteria. Subjects will also refrain from changing the use of any concomitant therapies during the duration of the study.

All new or modified concomitant therapy used during the study must be recorded.

Any new or modified concomitant therapy must be considered to determine if it is related to an AE. An AE must be reported unless the therapy is added or modified for non-medical reasons (*e.g.*, health insurance purposes) or it is for prophylaxis (*e.g.*, vaccinations).

A frequency of "as needed" (PRN) is not acceptable when reporting concomitant therapies.

4.5.3. Prohibited therapies

During this study, subjects are prohibited from using therapies listed in the exclusion criteria.

Starting with Visit 2 subjects are prohibited from applying any leave-on topical products, including but not limited to, lotions, creams, ointments, the investigator approved bland, non-medicated emollient/moisturizer and cosmetics to the treatment area within 8 hours prior to a study visit. The subject's routine cleansers are allowed.

The investigator should notify the Accutis, Inc. Medical Monitor within 24 hours if any prohibited therapy is required to ensure subject safety.

4.6. Subject Discontinuation from the Study

Subjects will be informed that they are free to withdraw from the study at any time and for any reason.

The investigator may remove a subject from the study if, in the investigator's opinion, it is not in the best interest of the subject to continue the study. Subjects may be discontinued due to occurrence of AEs, occurrence of pregnancy or use of a prohibited concomitant therapy. The investigator will notify the Accutis, Inc. study monitor within 24 hours of any subject discontinuation.

In case of premature discontinuation of study participation, efforts will be made to perform all the Visit 6 assessments for discontinuations during the treatment period and all the Visit 7 assessments for discontinuations during the no-treatment period. The date the subject is withdrawn from the study and the reason for discontinuation will be recorded on the subject's case report forms (CRFs). All withdrawn subjects with ongoing AEs will be followed as appropriate.

The study may be discontinued at the discretion of the investigator or Accutis, Inc. Some examples of reasons for discontinuation are the occurrence of the following:

- Increased frequency, severity or duration of known AEs
- Medical, regulatory or ethical reasons affecting the continued performance of the study
- Difficulties in the recruitment of subjects
- Cancellation of the drug development program.

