5.4.2. Visit 2 (Day 1); randomization and start of treatment period

This visit should occur within 14 days after Visit 1. Subsequent study visit dates must be scheduled based on the date of this visit.

Prior to this visit the investigator/designee must confirm that all items necessary to determine the subject's eligibility for randomization are available.

At this visit, the investigator or designee will perform the following procedures PRIOR TO RANDOMIZATION:

1. Query the subject in a non-directive manner about any changes in her/his health since the previous visit and report any changes that are, in the investigator's opinion, meaningful, as Medical History
2. Query the subject about any changes in her/his concomitant therapies since the previous visit and report changes on the appropriate form
3. Confirm the subject continues to comply with all study restrictions and has followed all study instructions
4. Measure vital signs
5. Perform a Lesion Count; a total of ≥ 10 and ≤ 40 inflammatory lesions (papules, pustules and nodules) and ≤ 2 nodules on the treatment area is required
6. Perform an IGA; a score of ≥ 3 (moderate to severe) is required
7. Determine the subject's eligibility for randomization
8. Discharge from the study subjects who are not eligible for randomization.

For subjects who are eligible for randomization the investigator or designee will perform the following procedures:

1. Take standardized color photographs
2. Have the subject perform a pre-treatment Local Tolerability Assessment (LTA)
3. Perform a pre-treatment LTA
4. Randomize eligible subjects
5. Dispense study medication to the subject
6. Instruct the subject on the proper study medication application technique
7. Observe the subject's first study medication application
8. Monitor the subject for at least 20 minutes after the Application Completion Time to detect any adverse events
9. Have the subject perform a post-treatment LTA 10 (± 4) minutes after the Application Completion Time
10. Perform a post-treatment LTA 20 (± 4) minutes after the Application Completion Time
11. Review the study instructions with the subject
12. Schedule Visit 3.

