5.4.5. Visit 5 (Day 57); treatment period follow-up

This visit should occur 56 [\pm 4] days after Visit 2.

At this visit, the investigator or designee will perform the following procedures:

1. Query the subject in a non-directive manner about any changes in her/his health since the previous visit and report all AEs on the appropriate form
2. Query the subject about any changes in her/his concomitant therapies since the previous visit and report changes on the appropriate form
3. Confirm the subject continues to comply with all study restrictions and has followed all study instructions
4. Perform a Lesion Count
5. Perform an IGA
6. Have the subject perform an LTA
7. Perform an LTA
8. Take standardized color photographs
9. Dispense and collect study medication as appropriate
10. Review the study instructions with the subject
11. Schedule Visit 6.

5.4.6. Visit 6 (Day 85); end of treatment period and start of no-treatment period

This visit should occur 84 [\pm 4] days after Visit 2.

At this visit, the investigator or designee will perform the following procedures:

1. Query the subject in a non-directive manner about any changes in her/his health since the previous visit and report all AEs on the appropriate form
2. Query the subject about any changes in her/his concomitant therapies since the previous visit and report changes on the appropriate form
3. Confirm the subject continues to comply with all study restrictions and has followed all study instructions
4. Perform a Lesion Count
5. Perform an IGA
6. Have the subject perform an LTA
7. Perform an LTA
8. Collect blood samples for clinical laboratory evaluations
9. Take standardized color photographs
10. Collect all study medication
11. Review the study instructions with the subject
12. Schedule Visit 7.

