5.4.7. Visit 7 (Day 99); end of study

This visit should occur 98 [\pm 4] days after Visit 2.

The investigator must review the Visit 6 clinical laboratory test results prior to this visit.

At this visit, the investigator or designee will perform the following procedures:

1. Query the subject in a non-directive manner about any changes in her/his health since the previous visit and report all AEs on the appropriate form
2. Query the subject about any changes in her/his concomitant therapies since the previous visit and report changes on the appropriate form
3. Confirm the subject continues to comply with all study restrictions and has followed all study instructions
4. Measure vital signs
5. Perform a urine pregnancy test for WOCBP
6. Perform a Lesion Count
7. Perform an IGA
8. Have the subject perform an LTA
9. Perform an LTA
10. Take standardized color photographs
11. Discharge the subject from the study.

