6.2.3. Vital signs

At Visits 1, 2 and 7, a qualified investigational center staff member will measure the following vital signs:

- Body temperature
- Pulse rate
- Respiration rate
- Blood pressure (systolic and diastolic) after the subject sits quietly for at least 5 minutes
- Height (at Visit 1 only)
- Weight (at Visit 1 only).

A systolic blood pressure >140mm Hg or a diastolic blood pressure >90mm Hg is considered abnormal and therefore the investigator must define the reading as CR or NCR.

A weight of >300 pounds is considered abnormal and therefore the investigator must define the reading as CR or NCR.

Any measure that is, in the opinion of the investigator, abnormal AND CR must be recorded as history if found prior to the start of the first study medication application or as an AE if found after the start of the first study medication application.

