6.2.4. Urine pregnancy tests

At Visits 1 and 7, the investigator or designee will perform a urine pregnancy test for subjects who are WOCBP. The urine pregnancy test kits used must have a minimum sensitivity of 25-mIU β -HCG/milliliter (mL) of urine.

Subjects who are WOCBP must have a negative pregnancy test result at Visit 1 to continue in the study.

If the result of any post-treatment urine pregnancy test is positive, the subject will be withdrawn from the study and the subject's pregnancy documented and followed.

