### **7.3. Subject Discontinuation**

Subjects will be informed that they are free to withdraw from the study at any time and for any reason. The investigator may remove a subject from the study if, in the investigator's opinion, it is not in the best interest of the subject to continue the study.

In case of premature discontinuation of study participation, efforts will be made to perform all the Visit 6 assessments for discontinuations during the treatment period and all the Visit 7 assessments for discontinuations during the no-treatment period.

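### Subjects who leave during treatment are sent to the Visit 6 assessments, which include neither vital signs nor (for women of childbearing potential) a pregnancy test, so neither has a scheduled post-dose value for them

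*Protocol*

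**What the plan says.** **Early discontinuation.** Protocol 4.6 states that "efforts will be made to perform all the Visit 6 assessments for discontinuations during the treatment period". SAP 7.3 carries the same instruction: "efforts will be made to perform all the Visit 6 assessments". The Visit 7 set is asked only of those who leave in the no-treatment period.

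**Visit 6.** The list under "Visit 6 (Day 85); end of treatment period and start of no-treatment period" (Protocol 5.4.6) has 12 items: adverse event query, concomitant therapies, compliance with restrictions, lesion count, IGA, the subject and investigator tolerability assessments, blood samples, photographs, collection of medication, review of instructions, and scheduling of Visit 7. Vital signs and the pregnancy test are not among them.

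**Vital signs.** Protocol 6.2.3: "At Visits 1, 2 and 7, a qualified investigational center staff member will measure the following vital signs". SAP 8.12.3 gives the same visits. At Visit 2 they belong to the block in Protocol 5.4.2 where staff "will perform the following procedures PRIOR TO RANDOMIZATION".

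**Pregnancy test.** Protocol 6.2.4: "At Visits 1 and 7, the investigator or designee will perform a urine pregnancy test for subjects who are WOCBP". The Visit 7 list in Protocol 5.4.7 confirms it: "Perform a urine pregnancy test for WOCBP".

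**What the plan promises.** The synopsis says that "vital sign readings and urine pregnancy tests will be monitored throughout the study", and that safety summaries will cover vital-sign changes from pre-application values. SAP 6.1.2 names both measures as safety endpoints. SAP 8.12.3 plans observed and change-from-baseline vital-sign summaries, with baseline at Visit 2 (SAP 8.5.1).

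**The concern.** Each section is clear by itself, and the visit lists agree with one another. The gap appears when the discontinuation rule is read against them: it sends treatment-period discontinuers to a visit that omits two of the five listed safety endpoints.

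These subjects need not be a random subset. Protocol 4.6 names adverse events as a reason for discontinuation. Protocol 5.6.8 removes subjects who cannot keep up twice-daily application to the whole treatment area for more than 4 consecutive days. Protocol 5.8.2 discharges anyone whose blind is broken. None is replaced (Protocol 4.8). Safety and tolerability are part of the main objective, yet the vital-sign change summary would describe only those who completed treatment or left afterwards. Missing values could therefore be related to how the product was tolerated.

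For a woman of childbearing potential who leaves during treatment, the only scheduled pregnancy test precedes any dose. Protocol section 8 requires notification if a subject may have been pregnant when exposed. For her, that would depend on suspicion or on a test nobody is scheduled to do.

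**Working it through.** The plan gives no figure to reproduce. The check is a cross-reading of the schedule, followed by an illustration of size.

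**Step 1. Scheduled values by visit** (Protocol 5.4.1 to 5.4.7, 6.2.3, 6.2.4)

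| Visit | Relation to first dose | Vital signs | Pregnancy test (childbearing potential only) |
|---|---|---|---|
| 1 | before | yes | yes |
| 2 | before (taken before randomization) | yes | no |
| 3, 4, 5 | after | no | no |
| 6 | after | no | no |
| 7 | after | yes | yes |

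**Step 2. Scheduled post-dose values per subject**

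| Subject | Last assessment set | Vital-sign sets | Pregnancy tests, if applicable |
|---|---|---|---|
| Completer | Visit 7 | 1 | 1 |
| Leaves in no-treatment period | Visit 7 set (Protocol 4.6) | 1 | 1 |
| Leaves in treatment period | Visit 6 set (Protocol 4.6) | 0 | 0 |

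**Step 3. Effect on the planned summary.** Change from baseline is the Visit 7 value minus the Visit 2 value, because Visit 7 is the only scheduled post-baseline vital-sign visit. A treatment-period discontinuer belongs to the safety population after one dose (SAP 8.2.2) but has no change score. Carry-forward (SAP 8.1) does not help: it applies to the MITT and PP analyses, and there is no post-dose value to carry.

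**Step 4. Timing**
- Visit 2 falls within 14 days after Visit 1, so the screening pregnancy test is up to 14 days before the first application.
- Visit 6 is at 84 ± 4 days and Visit 7 at 98 ± 4 days after Visit 2. The planned gap is 98 − 84 = 14 days; the shortest is 94 − 88 = 6 and the longest 102 − 80 = 22.
- A Visit 7 value is thus an off-treatment value. One taken soon after an early stop is not the same quantity.

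**Step 5. How many subjects.** The documents state neither a dropout rate nor the share of women of childbearing potential. Assume treatment-period dropout p of 5% to 20% and a share f of 20% to 60%.
- No post-dose vital signs: 36p = 36 × 0.05 = 1.8 to 36 × 0.20 = 7.2.
- By arm, if dropout is equal: 24p = 1.2 to 4.8 active; 12p = 0.6 to 2.4 vehicle.
- No post-dose pregnancy test: 36pf = 36 × 0.05 × 0.20 = 0.36 to 36 × 0.20 × 0.60 = 4.3.
- Each subject lost is 1/24 = 4.2% of the active arm or 1/12 = 8.3% of the vehicle arm.

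**The case against.** The strongest reply is that the plan is coherent as written. A discontinuer gets the same end-of-treatment set as a completer, and completers also have no vital signs or pregnancy test between the first dose and Visit 7. The synopsis wording is a loose summary of several measures.

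Much is also backstopped. Discontinuers keep the adverse event query, both tolerability assessments and the laboratory samples. Adverse events are reportable until the last visit or 30 days after the last application, whichever is longer. Abnormal, clinically relevant vital signs found off schedule are recorded as adverse events. Women of childbearing potential are told to call if they suspect pregnancy, and nothing bars an unscheduled test. The analyses at stake are descriptive: vital signs are summarized and pregnancy tests only listed.

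Most of this stands, and it limits the weight of the point. It does not supply the missing value. Event-driven reporting captures what someone notices; it does not fill a change-from-baseline table or replace a scheduled test. The comparison with completers also stops at Visit 6: completers go on to a scheduled post-dose value and discontinuers do not.

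Two further limits stand. The schedule tables (Protocol 5.3, SAP 6.2) are not in the readable text, so an early-termination column or footnote cannot be ruled out. If one exists, it would have to be reconciled with the written lists. The dropout and childbearing-potential ranges are assumptions, so the counts illustrate size and do not bound it.

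**Conclusion.** The point holds, as an inexpensive improvement and not a serious flaw. Followed exactly, the plan schedules 0 post-dose vital-sign sets for a treatment-period discontinuer against 1 for a completer, and 0 against 1 pregnancy test if she is of childbearing potential. This follows from the written text and needs no assumption beyond the absence of a contrary note in the unreadable schedule tables.

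Only the number affected depends on assumed rates: about 2 to 7 of 36 for vital signs, and about 0 to 4 for the pregnancy test. The primary analysis, the other efficacy analyses and adverse event reporting are unaffected. Subjects with adverse events who stay, and those who leave after treatment ends, remain in the vital-sign summary.

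**What to change.** Amend Protocol 4.6 and SAP 7.3, consistently with Protocol 5.4.6, 6.2.3 and 6.2.4, so that the early-discontinuation visit consists of the Visit 6 set plus the vital signs and, for women of childbearing potential, the urine pregnancy test already performed at Visit 7. Check that the schedule tables say the same.

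In SAP 8.12.3, state that early vital signs appear in a separate early-termination row with days since last application, not pooled with Visit 7. The early pregnancy test should likewise be identifiable in its listing (SAP 8.12.5) by days since last application, because it too lacks the off-treatment interval of Visit 7.

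**Cost.** One vital-sign set, with its 5-minute seated rest, per discontinuer seen; one test kit per woman of childbearing potential seen; one extra table row; and a short amendment with IRB approval. No visit is added.

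**Limits.** Protocol 4.6 promises only efforts, so nothing is recovered for subjects lost to follow-up. At any given dropout rate, the number of affected subjects is the most the change can recover. The early-termination row will hold few subjects and can only be read descriptively.
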